## **7.0 Study Design and Procedures**

### **7.1 Study Design**

[figure not shown]
This will be a single-center, open label, non-randomized Phase 0 feasibility trial to determine the neuro-pharmacokinetic/pharmacodynamic profile of posaconazole for HGGs. We will enroll 10 (5 for study group and 5 for control group) evaluable patients over 12 months with recent MRI findings suggestive of

high grade gliomas with need for surgical resection. Our historical surgical volume supports the feasibility of this proposal.

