#### 7.2.5 Visit 5 (Post-operative, Day 1)

##### Control group

The following will be performed as **routine (standard care)**:

- Neurological examination.

The following will be performed for the **research only**:

- Dialysate collection and blood sample collection.
- Collection of adverse events.

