### **Study Population**

Only patients who are eligible and take posaconazole according to protocol specifications (study drug arm only) **and** have undergone successful MDC implantation will be considered evaluable and included in the study analysis. Otherwise, enrolled patients will be replaced. All eligible patients for whom analyzable dialysate samples were obtained for at least 7 of the 9 time points will be considered evaluable for the primary study endpoint. Patients who are not evaluable will be replaced.

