### **Risks of microdialysis**

Microdialysis is an invasive surgical procedure with a small risk of bleeding at the site of insertion and discomfort for the patient. Removal of the catheter can result in minor discomfort as well. There is a chance that the catheter may break or get stuck in the brain that would require surgical intervention to remove it.

There is also a small risk of infection (1%), but pre-operative antibiotics are used to reduce the risk. However, this is a small device and it is removed early postoperatively, similar to other surgical drains placed postoperatively. There is also a very small possibility of bleeding along the catheter tip.

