## **14.0 Economic Burden to Subjects**

### **14.1 Costs**

There will be no additional costs to the participants for enrolling on the trial.

- The study drug, posaconazole, will be provided at no cost to the study drug group participants while they take part in this study.
- The research-related tests and procedures that will be provided at no cost to the participants include:
  - CMP at Visits 1, 2, and 5, including blood draws (study drug group only)
  - 12-lead ECG at Visit 2 (study drug group)
  - Physical examination at Visit 2 (study drug group)
  - Microdialysis catheter and related reagents, and catheter monitoring at visits 3 through 6 both groups)
  - The removal of the microdialysis catheter will also be at no charge, performed at the bedside (both groups)

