### **18.3 Causality and Severity Assessments**

The investigator will promptly review documented adverse events and abnormal test findings to determine 1) if the abnormal test finding should be classified as an adverse event; 2) if there is a reasonable possibility that the adverse event was caused by the study drug(s) or device(s); and 3) if the adverse event meets the criteria for a serious adverse event.

If the investigator's final determination of causality is "unknown and of questionable relationship to the study drug(s) or device(s)", the adverse event will be classified as associated with the use of the study drug(s) or device(s) for reporting purposes. If the investigator's final determination of causality is "unknown but not related to the study drug(s) or device(s)", this determination and the rationale for the determination will be documented in the respective subject's case history.

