### **18.7 Stopping Rules**

Trial accrual will be prematurely stopped if two or more unacceptable toxicities occur. Unacceptable toxicity is defined as mortality or grade 4 toxicity directly attributed to drug.

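### The only stopping rule with a threshold omits non-fatal grade 4 harm from the research catheter, and leaves unclear whether catheter-related deaths count

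*Combined protocol and SAP*

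**What the plan says.** **The rule.** Section 18.7 has two sentences. The first sets the threshold: "Trial accrual will be prematurely stopped if two or more unacceptable toxicities occur". The second defines the event: "Unacceptable toxicity is defined as mortality or grade 4 toxicity directly attributed to drug". Neither names a device or a procedure.

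**Who receives the catheter.** Section 7.1 gives the size: "We will enroll 10 (5 for study group and 5 for control group) evaluable patients over 12 months". Under Study Population in Section 8.2, patients who are eligible, who in the drug arm took posaconazole as specified, and who "have undergone successful MDC implantation will be considered evaluable and included in the study analysis"; others are replaced. Section 14.1 lists among the research-related items "Microdialysis catheter and related reagents, and catheter monitoring at visits 3 through 6 both groups". In Section 7.2.5 the control group's research-only procedures include "Dialysate collection and blood sample collection". Section 11.1 states that participants gain no direct benefit.

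**What can go wrong.** Section 10.0, Risks of microdialysis, lists bleeding, infection at 1%, and this: "There is a chance that the catheter may break or get stuck in the brain that would require surgical intervention to remove it". Only infection has a rate.

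**What is already recorded.** Section 7.2.4 collects adverse events related to catheter insertion in both groups. Section 18.3 assesses causality to drug or device. When the relationship is unknown and questionable, "the adverse event will be classified as associated with the use of the study drug(s) or device(s) for reporting purposes".

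**Other routes to stopping.** Sections 3.3.1 and 9.8 let the principal investigator end the trial at any time. Section 19.1.2 has the Cancer Institute Data Safety Monitoring Committee (CI DSMC) monitor data and safety, and has the coordinator notify it of unanticipated problems and serious adverse events. Section 9.6 schedules one cumulative data review, at study end.

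**The concern.** The rule is tied to an approved oral drug given to half the evaluable participants. It is silent on the invasive research procedure done in all of them. The plan foresees serious catheter complications, collects them and attributes them, yet the one rule that turns safety events into a trial-level action does not use that attribution. Two non-fatal grade 4 catheter injuries could occur with no stated criterion met, and accrual would continue unless someone chose to intervene.

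The definition is also open to two readings. The phrase about attribution to drug may qualify both *mortality* and *grade 4 toxicity*, or only the latter. Investigator and committee could therefore disagree on whether a catheter-related death counts, and would be settling the question after the event.

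**Working it through.** The plan states no operating characteristic for this rule, so there is no figure to reproduce. The check has three parts.

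**1. Which events count, under each reading of the definition**

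| Event | Attribution qualifies both terms | Attribution qualifies grade 4 only |
|---|---|---|
| Drug-attributed grade 4 event | counts | counts |
| Drug-attributed death | counts | counts |
| Catheter-attributed non-fatal grade 4 event, either group | does not count | does not count |
| Catheter-related death, drug group | does not count | counts |
| Catheter-related death, control group | does not count | counts |

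The third row is the same under both readings, so that gap is certain. The last two rows depend on the reading. The first reading is the more natural one, because the sentence defines a toxicity, but the grammar allows the second.

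**2. Exposure**

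- Evaluable participants: 5 drug + 5 control = 10.
- Evaluable participants with at least one catheter: 10 of 10, because successful implantation is a condition of being evaluable.
- Participants in whom a drug-attributed event is possible: 5 of 10.

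The figure of ten refers to evaluable participants. Enrolled patients whose intraoperative pathology is not high-grade glioma receive no catheter (Section 7.2.3). A patient who was implanted but later became non-evaluable and was replaced would add to the number exposed.

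**3. Size of the gap**

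Let p be the per-patient probability of a qualifying catheter event and n = 10, with patients independent.

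P(at least one) = 1 − (1 − p)^10

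P(two or more) = 1 − (1 − p)^10 − 10p(1 − p)^9

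The only rate in the documents is 1%, for infection of unspecified grade. The values of p below are assumptions.

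- p = 1%: P(at least one) = 1 − 0.9044 = 9.6%; P(two or more) = 1 − 0.9044 − 0.0914 = 0.4%.
- p = 5%: P(at least one) = 1 − 0.5987 = 40.1%; P(two or more) = 1 − 0.5987 − 0.3151 = 8.6%.
- p = 10%: P(at least one) = 65.1%; P(two or more) = 26.4%.

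Under the present text the contribution of non-fatal catheter events to the count is zero at every p. If the count of two were extended to catheter events in both groups, the P(two or more) figures give the chance that catheter events alone would stop accrual. One drug event plus one catheter event would also meet an extended rule. The documents give no rate for drug events, so that part is not computed.

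**The case against.** The strongest reply is that catheter harm is not unwatched. Section 19.1.2 gives the CI DSMC a monitoring role and has serious adverse events notified to it, without limiting this to drug, group or grade. A catheter haemorrhage or a retained catheter needing surgery could well meet the seriousness definition in Section 18.1. Section 19.1.1 adds monitors who review adverse events. This stands. A reader might infer that catheter harm cannot stop the trial, or that everything outside Section 18.7 is left to the principal investigator. The documents support neither. What is missing is a stated criterion. The single cumulative review at study end does not supply one, and neither does the provision in Section 7.2.4 that cancels microdialysis for an individual patient.

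A reader might also infer that the count is zero in every catheter scenario and that controls can never contribute. That fails for deaths if *mortality* means death from any cause.

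A third tempting reading is that Section 18.7 contradicts Section 18.3 by not counting events of questionable relationship. Section 18.3 limits that category to reporting, and a broad net for reporting can coexist with a stricter test for halting accrual. Counting every questionable grade 4 event after open glioma resection could stop a ten-patient trial on background surgical morbidity. This objection stands, and the fix respects it.

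The reply can add that these catheters are described in Section 2.3 as approved and routinely placed, and that they are removed on postoperative day 2. This lowers the expected rate but does not put the events inside the rule. Nor do the documents say that the principal investigator's own group places the catheters. Section 7.2.3 refers only to the neurosurgeon, so no conflict-of-interest argument is made here.

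Finally, an extended rule would rarely be met at low event rates. This is true and limits the weight of the point.

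**Conclusion.** The concern holds in limited form. On either reading, non-fatal grade 4 harm attributed to the catheter lies outside the only stopping rule with a threshold, although all ten evaluable participants are exposed and only five of them take the drug. Whether catheter-related deaths count is ambiguous and needs a decision.

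The practical size is modest: a 0.4% to 8.6% chance of two or more catheter events in ten, if the per-patient risk is 1% to 5%. That range is assumed, patients are taken as independent, and the only documented figure is 1% for infection. The defect is therefore one of scope and clarity, not a large loss of detection power. It deserves correction because the change is small and the plan already collects the information that a corrected rule would use.

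**What to change.** Reconcile Section 18.7 with Section 18.3 in one paragraph:

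- Keep the existing count of two, and let it cover qualifying events attributed to the study drug or to the catheter or study procedure, in either group.
- State whether *mortality* carries the attribution qualifier or means death from any cause.
- Leave to the sponsor and the CI DSMC the level of attribution needed when the relationship is questionable, and write their decision into Section 18.7.

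The cost is the wording and a slightly higher chance that accrual stops early. From catheter events alone, that chance is the two-or-more probability given above (0.4% at an assumed 1% risk, 8.6% at 5%). No new data collection, committee or threshold is needed.

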## **19.0 Study Monitoring, Auditing and Inspecting**

### **19.1 Study Monitoring Plan**

#### **19.1.1 Quality Assurance and Quality Control**

The study will be monitored by Clinical Trial Monitoring Team from the Department of Public Health Sciences at Penn State Hershey College of Medicine.

Staff within the Department of Public Health Sciences will be monitoring the study for protocol compliance, data quality, and regulatory compliance. This will include reviewing the informed

consent process and completed forms, verifying the presence of essential documents in the study regulatory binder, completing source document verification for data entered into REDCap, ensuring the study is implemented as planned, reviewing adverse events and the reporting of serious adverse events, and ensuring that all data quality rules have been executed and resolved and all data queries are resolved and closed.

The monitor will create a detailed report following each scheduled monitoring session to forward to the PI and will verify that proposed action items are addressed and completed. The monitoring will occur at regular intervals as specified in the monitoring plan developed by Public Health Sciences and PSU Sponsor Investigator.

#### **19.1.2 Safety Monitoring**

Data and safety will be monitored by the Cancer Institute Data Safety Monitoring Committee (CI DSMC).

The Principal Investigator will confirm that all adverse events (AE) are correctly entered into the AE case report forms by the coordinator; be available to answer any questions that the coordinators may have concerning AEs; and will notify the IRB, FDA, and/or DSMB of all applicable AEs as appropriate. All assessments of AEs will be made by a licensed medical professional who is an investigator on the research.

The Research Coordinator will complete the appropriate report form and logs; assist the PI to prepare reports and notify the IRB, and CI DSMC of all Unanticipated Problems/SAE's.

The Monitor will confirm that the AEs are correctly entered into the case report forms. The Monitor will also confirm that the adverse events are consistent with the source documents and are reported to the appropriate regulatory bodies as required.

### **20.0 Future Undetermined Research: Data and Specimen Banking**

#### **20.1 Data and/or specimens being stored**

Not applicable

#### **20.2 Location of storage**

Not applicable

#### **20.3 Duration of storage**

Not applicable

#### **20.4 Access to data and/or specimens**

Not applicable

#### **20.5 Procedures to release data or specimens**

Not applicable

#### **20.6 Process for returning results**

Not applicable

## 22.0 Confidentiality, Privacy and Data Management

See the Research Data Plan Review Form
